**Sample size estimates**

Separate from this readout, a blinded statistician will generate sample size estimates for reaching the pre-specified statistical thresholds for inferiority and equivalence (at the 5 pre-specified levels) between C+I and S, based on the results seen in this report.

11-9-2021	DHHS/FDA provides mAb EUAs and treatment for COVID-19 eligibility criteria	
Eligibility Criteria - High risk is defined as patients who meet at least one of the following criteria:
 
 • Have a body mass index (BMI) $\geq 35^a$ • Have chronic kidney disease • Have diabetes • Have immunosuppressive disease^b • Are currently receiving immunosuppressive treatment • Are ≥ 65 years of age • Are ≥ 55 years of age AND have cardiovascular disease, OR hypertension, OR chronic obstructive pulmonary disease/other chronic respiratory disease. • Are 12–17 years of age AND have BMI $\geq 85^a$th percentile^a for their age and gender based on CDC growth charts,^a OR sickle cell disease, OR congenital or acquired heart disease, OR neurodevelopmental disorders, for example, cerebral palsy, OR a medical-related technological dependence, for example, tracheostomy, gastrostomy, or positive pressure ventilation (not related to COVID-19), OR asthma, reactive airway or other chronic respiratory disease that requires daily medication for control. 
EUAs for
 
 • bamlanivimab • bamlanivimab and etesevimab (available 09-02-2021) • casirivimab and imdevimab
03-10-2021	UPMC – Opened study enrollment	Go-live date for trial with bamlanivimab, and casirivimab and imdevimab only and following COVID-19 Treatment Guidelines.
03-16-2021	UPMC - Incorporation of bamlanivimab-etesevimab into random allocation	Start incorporating bamlanivimab and etesevimab into most sites. There was a 1-week delay to use etesevimab at six sites due to low initial supply.
02-23-2021	UPMC - mAb treatment expanded to Emergency Departments	Based on published data from our health system demonstrating significant decrease in hospitalizations and deaths with bamlanivimab, the decision was made to invest resources in Emergency Department expansion to increase access to mAb treatment.
03-25-2021	DHHS/FDA EUA for distribution of bamlanivimab alone was halted	A memorandum on the Fact Sheet for bamlanivimab alone – Update was issued on 03/17/21. Pseudovirus neutralization data for SARS-CoV-2 variant substitutions with bamlanivimab alone was unsuccessful.
3-31-2021	UPMC – halted bamlanivimab alone	Emerging data about lack of efficacy with SARS-CoV-2 variants resulted in System COVID-19 Pharmacy & Therapeutics Committee's decision to remove bamlanivimab alone from formulary. All sites put on view to use bamlanivimab only with etesevimab.
04-16-2021	DHHS/FDA EUA for bamlanivimab was revoked	EUA revoked due to lack of efficacy with SARS-CoV-2 variants.
04-25-2021	UPMC - Protocol Amendment 1 to remove use of bamlanivimab alone	Updated trial protocol to reflect clinical practice of no longer using bamlanivimab alone.
04-26-2021	UPMC – expanded study enrollment to observation status patients	Established process for treating observation status patients at UPMC hospitals.
05-06-2021	UPMC - Interim Analysis	Data supported it was safe to proceed.
05-14-2021	DHHS/FDA EUA expands eligibility criteria	
Eligibility Criteria - The following medical conditions or other factors may place adults and pediatric patients (age 12–17 years and weighing at least 40 kg) at higher risk for progression to severe COVID-19:
 
 • Older age (for example age ≥ 65 years of age)

Date	Change	Explanation
		
 • Obesity or being overweight (for example, adults with $\text{BMI} > 25 \text{ kg/m}^2$^a or if age 12–17, have $\text{BMI} \geq 85\text{th}$ percentile^a for their age and gender based on CDC growth charts) • Pregnancy • Chronic kidney disease • Diabetes • Immunosuppressive disease^b or immunosuppressive treatment • Cardiovascular disease (including congenital heart disease) or hypertension • Chronic lung diseases (for example, chronic obstructive pulmonary disease, asthma [moderate-to-severe], interstitial lung disease, cystic fibrosis, and pulmonary hypertension) • Sickle cell disease • Neurodevelopmental disorders (for example, cerebral palsy) or other conditions that confer medical complexity (for example, genetic or metabolic syndromes and severe congenital anomalies) • Having a medical-related technological dependence (e.g., tracheostomy, gastrostomy, or positive pressure ventilation [not related to COVID-19])
05-26-2021	DHHS/FDA provides an EUA for sotrovimab	Sotrovimab is a new mAb treatment.
06-03-2021	DHHS/FDA EUA revised to decrease dose for casirivimab and imdevimab	Casirivimab 600mg and imdevimab 600 mg
06-15-2021	UPMC - decreased dose for casirivimab and imdevimab	Casirivimab and imdevimab dose decreased from 2400 mg to 1200 mg.

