16. CONDUCT

17. DATA COLLECTION

The EUAs require that healthcare facilities and providers report therapeutic information and utilization data through HHS Protect, Teletracking, or National Healthcare Safety Network as directed by the US Department of Health and Human Services.

We will collect data including baseline demographics and underlying conditions, results of SARS-CoV-2 PCR or antibody testing, and initial care including mAb infusion completion. We will collect post-randomization healthcare encounters, including hospitalization, emergency department visits, ICU care, and other measures of healthcare utilization. We will use an electronic health record data collection process to augment existing UPMC data collection processes, as necessary.

All data will be handled and secured as per University of Pittsburgh and UPMC data guidelines.

There will be no research activities involving direct interaction with subjects performed as part of this evaluation.

In addition to the primary and secondary outcome data referenced in this submission, data collected will include the below areas. All data will be abstracted directly from the electronic health record and handled anonymously.

- mAb was administered, including date, time, and infusion completion as well as the location of the infusion
- Demographics (including age, sex, race, body weight, vaccination status)
- Healthcare encounters, including hospital and ICU admission status if applicable
- Medication usage and doses
- Hospital and ICU admission status, if applicable
- Administration of medications related to COVID-19, if applicable
- Remnant blood availability
- Laboratory and microbiology data, including COVID-19 testing done for clinical purposes

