Using Pennsylvania statewide data, we will estimate the prevalence of a given variant type by time. Then, we can categorize patients into various time epochs relative to the variant prevalence. These categories will be provided based upon the changing distributions over time in our region.

To consider the internal validity of this “surrogate” approach, we will use data from the subset of patients with actual genotype sequencing, compare the proportion of patients with prevalence of the variant type of interest across levels of the surrogate classification (i.e., Cochran Mantel-Haenszel test of trend).

Adaptive Analyses Reporting

The primary analysis will read out with summaries of the potential arm triggers for each arm actively in the “regimen space.” These summaries will include the probability each mAb is optimal in the active regimen space and the randomization probabilities.

A second analysis will be conducted with all arms (even those closed) in the regimen space, to report the probability each regimen is optimal among the larger regimen space.

As the EHR system contains the same covariate and baseline data for both mAb treated and untreated patients, we have continuously updated flags for each patient in the system as being “mAb eligible” (or not) based on EUA criteria on the date the patient became COVID-19 positive. With appropriate selection, this affords 2 untreated control groups for analysis that we will describe using mean (SD), median [IQR}, and proportions, as appropriate: mAb eligible patients who were never randomly assigned to a respective mAb regimen, and mAb eligible patients who were randomly assigned to a mAb regimen yet did not receive treatment.

Readout

Introduction

This document describes the detail of the analysis read-out from July 26, 2021. This document is an appendix to the Statistical Analysis Plan for the “UPMC Antibody Treatment and Evaluation Center” with the details for this analysis read-out.

- We will analyze and report three treatment arms (below) as the first two have been administratively closed to enrollment due to FDA decisions.
- Unblinded data from this and prior interim analyses can be shared with investigators after the last randomized allocations (June 25) to the two mAb treatment arms closed by FDA.

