- This unblinding is appropriate as future analyses of patients randomized to the third arm (C+I) will not be compared to the first two arms, there are no “control” arms as all patients receive mAb treatment, and future comparisons will be of C+I vs newer mAbs.

- Enrollment continues in the currently available treatment arms (C+I and S). “S” refers to sotrovimab, produced by GSK and Vir.

Treatment Arms

There are three treatment arms that will be included in this analysis. The treatment arms are

1. B (Bamlanivimab)
2. B+E (Bamlanivimab/Etesevimab combination)
3. C+I (casirivimab/imdevimab combination)

Primary Endpoint

The primary endpoint for this read-out is hospital-free days.

Primary Analysis Population

The primary analysis population for this read-out is the “As-Infused” population. This analysis will include each patient randomized from March 10, 2021 until June 25, 2021. The date of the data set snapshot is on July 26, 2021.

Primary Analysis Model

The primary analysis model is as described in the trial SAP.

The primary analysis for the primary endpoint is a cumulative proportional odds model. Let the probability of an outcome of less than or equal to y be $\pi_y = \Pr(Y \leq y)$. Let a be the indicator of treatment arm ($a=1,\dots,k$). The model adjusts for the following baseline variables:

- ED or infusion center (0=infusion center, 1=ED)
- Age (with categories of <30, 30-39, 40-49, 50-59, 60-69, 70-79, and ≥ 80 ; 60-69 will be used as the referent)
- Sex (sex at birth, male is the referent)
- Covid variant is not modeled in this primary analysis
- Time (two-week epochs of time are used for adjustments; the most current 4-week period is the referent)

The primary analysis model is based on a cumulative logistic regression, where $\pi_y = \Pr(Y \leq y)$, where

$$\log\left(\frac{\pi_y}{1-\pi_y}\right) = \alpha_y - \theta_a \delta_{[a]} - \sum_{v=1}^4 \beta_{vj} \delta_{vj} - \lambda_{[time]}; \quad y = -1, 0, 1, 2, \dots, 27.$$

The additive covariate effects across all treatment arms for each patient are modeled through the β parameters. The δ parameters are indicator functions for the treatment arm and covariate values for the baseline covariates. The efficacy of the treatment arms is modeled with the θ parameters. The ordinal effect parameters (α_y) are modeled with a Dirichlet distribution with equal weight on each outcome and a sum of 1.

The baseline covariate effects are modeled with independent weak prior distributions:

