Combination Futility: For comparing B+E to B the combination (B+E) will be compared to the individual component arm (B). If there is more than a 95% probability that the effect of the combination B+E is no better than a 20% improvement in the odds ratio compared to B, then the combination will be declared *not clinically relevantly superior (combination futile)* to N.

Modeling Treatment Heterogeneity Across Variant Date Prevalence Epochs

For this read out, the following time epochs will be modeled with different treatment effects using the Treatment Heterogeneity analysis model.

The treatment effect, θ_a , will be modeled separately within each epoch, $s = 1, \dots, S$, as $\theta_{a1}, \theta_{a2}, \dots, \theta_{aS}$, with hierarchical prior distribution:

$$\theta_{as} \sim N(\mu_a, \tau_a^2), a = 1, \dots, 3; s = 1, \dots, S.$$

$$\mu_a \sim N(0, 10^2); \tau_a^2 \sim IG(0.25, 0.1).$$

The following time epochs are specified:

1. March 10 - March 31
2. April 1 - April 30
3. May 1 - May 31
4. June 1 - June 25

Specific Analyses

#	Status	Population	Endpoint	Other
1	Primary	As-Infused to B, B+I, or C+I on or before June 25, 2021	HFD	
2	Variant Secondary	As-Infused to B, B+I, or C+I on or before June 25, 2021	HFD	Differential efficacy by time epoch specified

The Primary Analysis

Quantity of Interest	Posterior Probability
B+E superior to B	
B+E combination futile to B	
C+I superior to B	
C+I superior to B+E	

Statistical Triggers Met for Equivalence with Delta Ranges of Equivalence

Odds-Ratio Parameter	Mean	SD	Median	95% Credible Interval
Age < 30				
Age 30 – 39				
Age 40 – 49				
Age 50 – 59				
Age 60 – 69	1			
Age 70 – 79				
Age 80+				
Female				
Time Bucket 1				
...				
Time Bucket k-1				
Referent Arm	1			
Arm #2				
Arm #3				
Arm #2/Arm #3				

Graphical summaries

1. Stacked bar plots and cumulative distributions of HFDs by treatment arm
2. Stacked bar plots and cumulative distributions of HFDs by time epochs
3. Stacked bar plots and cumulative distributions of HFDs by sex
4. Stacked bar plots and cumulative distributions of HFDs by treatment arm by time epoch

The Variant Secondary Analysis

Quantity of Interest	Posterior Probability
B+E superior to B	
B+E combination futile to B	
C+I superior to B	
C+I superior to B+E	

Statistical Triggers Met for Equivalence with Delta Ranges of Equivalence

Odds-Ratio Parameter	Mean	SD	Median	95% Credible Interval
Age < 30				
Age 30 – 39				
Age 40 – 49				
Age 50 – 59				
Age 60 – 69	1			

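### In the July read-out, variant epoch 4 (June 1-25) spans the June 15 change in C+I dose, and the epoch model has no term for dose

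*Combined protocol and SAP*

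**What the plan says.** **Dose.** The timeline of changes records an EUA revision on June 3, 2021 ("Casirivimab 600mg and imdevimab 600 mg") and the health system's own change on June 15, 2021: "Casirivimab and imdevimab dose decreased from 2400 mg to 1200 mg".

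**Window and arms.** For the July 26, 2021 read-out, the Primary Analysis Population section states: "This analysis will include each patient randomized from March 10, 2021 until June 25, 2021". Its Treatment Arms section lists B, B+E and C+I. C+I has one entry, without a dose.

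**Variant epochs.** The SAP section Assessment of COVID-19 Variants introduces calendar time as a surrogate for variant type, because many patients will lack sequencing: "we can categorize patients into various time epochs relative to the variant prevalence". The read-out applies this under the title "Modeling Treatment Heterogeneity Across Variant Date Prevalence Epochs". Each arm's effect "will be modeled separately within each epoch", with a hierarchical normal prior across epochs. The epochs are March 10-31, April 1-30, May 1-31 and June 1-25.

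**Dose in the analysis.** Protocol section 17 (Data Collection) lists "Medication usage and doses" among the collected items. The July read-out's model, its Specific Analyses table and its result tables do not use dose.

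**The concern.** The primary hypothesis (protocol section 6) includes variation of effect by SARS-CoV-2 variant, and the epoch analysis is the July read-out's only listed analysis of that question. Within June, the C+I regimen changed for a reason unrelated to the variant mix. The model has one C+I parameter for the whole of June 1-25, so that parameter averages over two doses. If the C+I versus B+E contrast in epoch 4 differs from earlier epochs, a reader guided by the section title would probably think of variants first, and nothing in the planned output would show whether dose contributed.

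Nothing else in the plan removes the ambiguity:

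- The time adjustment is common to all arms, and its most recent bucket covers four weeks. It cannot absorb a change specific to C+I.
- The check against genotyped patients asks whether variant prevalence tracks the epochs. It can succeed fully while dose also changes within an epoch.
- Variant is not a covariate in the July primary model.

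The plan does treat a change in how C+I is given as relevant elsewhere. The October read-out excludes subcutaneous C+I from its primary analysis so that arms are compared by the same route. The July appendix is dated about six weeks after the dose change, so a comparable step could have been written in.

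**Working it through.** The plan states no figure for this point that could be reproduced, so the check is date arithmetic, an illustration of size, and a test of what the data could separate.

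**Inputs**

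- Analysis window: March 10 to June 25, 2021 (July read-out, Primary Analysis Population).
- Epoch 4: June 1 to June 25 (July read-out, list of epochs).
- Dose change: June 15, from 2400 mg to 1200 mg (timeline), a ratio of 1200/2400 = 0.50. The June 3 entry agrees with the later total: 600 + 600 = 1200 mg.
- Dose effect and counts by dose: not given. The odds ratios below are assumptions.

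**Step 1: overlap**

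- Window: 22 + 30 + 31 + 25 = 108 days.
- Epoch 4: 25 days, of which June 1-14 is 14 days and June 15-25 is 11 days.
- Share of epoch 4 from the change onward: 11/25 = 0.44.
- Share of the whole window: 11/108 = 0.10.
- Epochs 1 to 3 lie wholly before the change.
- Most recent time bucket: if the last analysed infusion was on June 25, four weeks back gives May 29 to June 25, which again holds both doses.

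**Step 2: illustration of size**

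Let r be the odds ratio for later versus earlier C+I dose, with no variant effect. If a share s of C+I patients received the later dose, the apparent odds ratio is about r^s, ignoring the hierarchical prior. With even accrual:

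| Assumed r | Epoch 4, r^0.44 | Pooled, r^0.10 |
|---|---|---|
| 0.70 | 0.85 | 0.96 |
| 0.80 | 0.91 | 0.98 |
| 0.90 | 0.95 | 0.99 |

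An r above 1 acts the other way: 1.25^0.44 = 1.10.

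Even accrual may overstate s, since the protocol's Rationale describes case volumes as falling in June 2021. If daily C+I accrual on June 15-25 were half that of June 1-14, then s = 5.5/(14 + 5.5) = 0.28, and r = 0.80 gives 0.80^0.28 = 0.94.

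**Step 3: is separation possible?**

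The planned epoch-by-arm layout for C+I and B+E has 8 columns and rank 8. Adding a C+I dose indicator from June 15 and a period term common to both arms gives 10 columns and rank 10. A dose contrast is therefore estimable, because the read-out gives June 25 as the last allocation date for the arms closed by FDA, so B+E served as a concurrent comparator. Two limits apply.

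- *Interpretation.* Within C+I, dose and calendar period change on the same date. The contrast isolates dose only if the variant-by-arm effect is constant within June, which is the very effect in question.
- *Precision.* Assume 100 to 400 C+I plus B+E patients in epoch 4, split evenly, and a binary outcome with event rate p of 10 to 20%. Then SE = sqrt(2/(n_pre·p(1-p)) + 2/(n_post·p(1-p))), where n_pre and n_post are the per-arm counts.
  - 100 patients, p = 0.10: n_pre = 28, n_post = 22, SE = 1.34, 95% factor exp(1.96 × 1.34) = about 14.
  - 400 patients, p = 0.20: n_pre = 112, n_post = 88, SE = 0.50, 95% factor about 2.7.

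The 95% interval would span a factor of about 2.7 to 14 either side of the estimate.

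**The case against.** Several arguments against the point have force.

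- **Scope.** Only C+I in one of four epochs of a secondary analysis is directly affected. This stands. The hierarchical prior passes a little of any shift to the other C+I epochs, and it also shrinks the epoch-4 shift itself, so the values in the working are upper illustrations for a given r.
- **Assumed size.** No dose effect appears in the documents, and the 44% is a share of days, not of patients. This stands. Figure S3 is described as showing infusions over time, but its content was not available for this check.
- **No stated rule.** The plan nowhere says that each epoch difference will be attributed to variants. Its Specific Analyses table speaks of differential efficacy by time epoch, and the SAP names sequenced variant as its first approach. This partly stands. However, the section title ties the epochs to variants, and the sequenced subgroup is not among the July analyses.
- **Pragmatic arm definition.** C+I as authorised over time is a legitimate arm in a study that expects treatments to follow FDA decisions. This stands for the pooled comparison. It does not help when the question is why one epoch differs from another.

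Three stronger readings are tempting, and the documents do not support them.

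- A reader might infer that the mixture carries into the comparison of C+I with sotrovimab, because the SAP lets later inferences use all data. The October read-out excludes everyone infused before July 14, so all its C+I patients were treated after the change.
- A reader might infer that dose and variant can never be told apart. That is true of the planned model only. The data allow a run with dose held constant.
- A reader might infer that separate C+I arm codes, or a split of epoch 4 at June 15, would resolve the matter. Neither separates dose from calendar period within C+I.

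**Conclusion.** The point holds for the variant-epoch secondary analysis of the July read-out. Epoch 4 mixes two C+I doses (14 days before and 11 days from the change), the model has no term that distinguishes them, and a shift in epoch-4 contrasts with C+I is therefore open to more than one explanation. Concurrent randomised contrasts in that epoch remain valid for the dose mix given; what is in doubt is attributing a difference between epochs to variants.

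The size cannot be determined. Under even accrual, without shrinkage and with an assumed dose odds ratio of 0.80, the epoch-4 shift is about 0.91 and the pooled shift about 0.98; slower accrual after June 15 or shrinkage would make the epoch-4 shift smaller. The pooled primary comparison is little affected and the October read-out is not affected. This is a cheap improvement to interpretation, not a defect that overturns the read-out. It implies no view on either dose.

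**What to change.** Add to the July read-out:

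1. One sensitivity run of the epoch model, and of the C+I contrasts, restricted in all arms to patients infused before June 15, so that epoch 4 becomes June 1-14. Restricting all arms keeps the comparison concurrent. Keep the calendar boundaries of the time buckets as in the main run; otherwise counting back four weeks from June 14 would move the referent bucket to May 18-June 14 and add a second difference between the runs.
2. The number of C+I patients in epoch 4 by recorded dose, which also checks the June 15 cut-off against actual administration.
3. A sentence stating that an epoch-4 difference will not be attributed to variants unless it persists in that run.

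The cost is one extra run and one tabulation from data already collected. The downside is precision. With even accrual and before shrinkage, the epoch-4 interval on the log-odds scale widens by about sqrt(25/14) = 1.34, or 34%; the pooled interval widens by about sqrt(108/97) = 1.055, or 5.5%. An epoch-4 difference that fades in the restricted run should be reported as unresolved, since lost precision could also explain it.

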Charlson Comorbidity Index ^b	1166	1.1 (1.5)	299	0.8 (1.1)
..				
Age in years (categories)	1935	..	443	..
0 to 30	..	157 (8.1)	..	59 (13.3)
31 to 50	..	511 (26.4)	..	132 (29.8)
51 to 60	..	484 (25.0)	..	84 (19.0)
61 to 70	..	474 (24.5)	..	92 (20.8)
71 to 80	..	218 (11.3)	..	44 (9.9)
81 and older	..	91 (4.7)	..	32 (7.2)
Female sex ^c	1935	1041 (53.8)	443	274 (61.9)
Race ^d	1884	..	428	..
White	..	1498 (79.5)	..	345 (80.6)
Black	..	335 (17.8)	..	79 (18.5)
Other ^e	..	51 (2.7)	..	4 (0.9)
Body mass index (categories) ^g	1302	..	306	..
Less than 18.5	..	7 (0.5)	..	7 (2.3)
18.5 to less than 25.0	..	119 (9.1)	..	27 (8.8)
25.0 to less than 30.0	..	273 (21.0)	..	51 (16.7)
30.0 to less than 35.0	..	309 (23.7)	..	75 (24.5)
35.0 to less than 40.0	..	296 (22.7)	..	68 (22.2)
40.0 or higher	..	298 (22.9)	..	78 (25.5)
History of hypertension	1414	782 (55.3)	352	152 (43.2)
History of obstructive sleep apnea	1414	370 (26.2)	352	81 (23.0)
History of allergic rhinitis	1414	189 (13.4)	352	49 (13.9)
History of diabetes	1414	383 (27.1)	352	63 (17.9)
History of coronary artery disease	1414	172 (12.2)	352	35 (9.9)
History of congestive heart failure	1414	117 (8.3)	352	32 (9.1)
History of atrial fibrillation	1414	102 (7.2)	352	20 (5.7)
History of valvular heart disease	1414	97 (6.9)	352	26 (7.4)
History of stroke	1414	84 (5.9)	352	22 (6.2)
History of dyspnea	1414	105 (7.4)	352	20 (5.7)
History of asthma	1414	517 (36.6)	352	136 (38.6)
History of chronic obstructive pulmonary disease	1414	278 (19.7)	352	78 (22.2)
History of chronic kidney disease	1414	112 (7.9)	352	27 (7.7)
History of fatty liver disease	1414	83 (5.9)	352	14 (4.0)
History of viral hepatitis	1414	40 (2.8)	352	6 (1.7)
History of cancer	1414	186 (13.2)	352	32 (9.1)

^aCalculated as weight in kilograms divided by height in meters squared.

[figure not shown]
^bCharlson Comorbidity Index is calculated as S – result from point addition; CCI ten year survival=0.983^A where A=e^(S x 0.9).

^cSex was reported by the patients.

^dRace was reported by the patients.

[figure not shown]
^eOther includes Chinese, Filipino, Hawaiian, American Indian/Alaskan Native, Asian, Hawaiian/other Pacific Islander, Middle Eastern, Native American, or Pacific Islander.

Figure S1: Treatment Heterogeneity Across Variant Date Prevalence Epochs

[figure not shown]
Red represents worse outcomes and blue represents better outcomes.

Figure S2: SARS-CoV-2 Variants of Concern Proportion in Pennsylvania During the Study (March 10–June 25, 2021)

[figure not shown]
Red represents Alpha B.1.1.7, purple is Beta B.1.351, green is Delta B.1.617.2, and blue is Gamma P.1.

Figure S3: Number of Infused Patients Over Time and Distribution of Patients Within Each of the Time Buckets Used to Estimate Time Trends in the Analysis Model (Primary Analysis)

The time buckets are derived so that the first bucket is the most recent 4 weeks going backwards in time from the most recently infused patient in the dataset that has a complete hospital-free days outcome. Thereafter, each bucket is defined as the next 2-week interval backwards in time. The vertical dashed line indicates the infusion date for the last patient who has passed 28 days and has a known outcome on the primary endpoint at the time of this analysis.

Figure S4: Stacked Proportion of Hospital Free Days for Each Time Epoch (Primary Analysis; As-infused Population)

Red represents worse outcomes and blue represents better outcomes.

Study Protocol
Final Version 1.3, June 30, 2021

UPMC OPTIMISE-C19 (OPtimizing Treatment and Impact of Monoclonal antIbodieS through Evaluation for COVID-19)

A Pragmatic Evaluation of Monoclonal Antibody Treatments in Participants with COVID-19 Illness (ClinicalTrials.gov, NCT04790786)

Summary of Protocol Changes for Amendment on April 25, 2021

Page #	Protocol Section	Reason for Change
1	Protocol Title Page	Title changed to reflect new abbreviation being used for study
2-3	Summary Table	Summary table updated to reflect protocol changes
10	4.1	Clarification added to section 4.1 to reflect changing landscape of FDA EUA and revocation
12	5	Clarification added to section 5 to reflect changing landscape of FDA EUA and revocation
12	5.1	Removed section 5.1 bamlanivimab due to EUA revoked
17	8.1	Updated to provide more detail on the monitoring of data by UPMC clinical leadership
18	9	EUA for bamlanivimab removed

Summary of Protocol Changes for Amendment on June 30, 2021

Page #	Protocol Section	Reason for Change
NA	NA	Minor administrative changes throughout the document to reflect Amendment #2 documentation
2-3	Summary table	Summary table updated to reflect protocol changes
7	2.1.	Information regarding new monoclonal antibody sotrovimab
7	2.1.	Information added regarding the revocation of EUA approved of bamlanivimab and etesivimab
8	2.2.	Information added to reflect current COVID trends
10-11	4.1.1.	Updated Inclusion Criteria as per EUA requirements
12	5	Information added regarding the revocation of EUA approved of Bamlanivimab
12	5.1.	Removal of section 5.1. – bamlanivimab and etesivimab
12-13	5.2.	Addition of newly approved monoclonal antibody – sotrovimab
15	6.3.	Information added to reflect UPMC will utilize a pharmacy manual if provided by the drug manufacturer
19	9.0.	Exhibits added and removed to reflect current EUA approved monoclonal antibodies

Protocol Summary

Background	
• FDA Emergency Use Authorization (EUA) exists for multiple monoclonal antibodies (mAb) to treat COVID-19; the EUAs stipulate eligibility criteria, patient-physician communication, and clinical monitoring.• UPMC provides mAbs as routine care; physicians order a mAb infusion and pharmacies assign whichever mAb is available under a therapeutic interchange approach. If scarcity exists, a lottery system is used.• Physicians review with patients the EUA Fact Sheet for each mAb and explain they could be assigned any of the EUA-governed mAbs.
Approach	
• Structure the therapeutic interchange policy and lottery system using a UPMC pharmacy embedded assignment system that allows a comparative effectiveness evaluation of the multiple mAbs.• Collect data from clinically performed UPMC processes and EUA requirements for routine care.
Treatments	
• Monoclonal antibodies (mAb) for COVID-19
Inclusion Criteria	
These criteria are as per the FDA EUAs for COVID-19 mAbs as of June 2021.
 
• Adult (\geq 18 years old)• Children \geq 12 years old weighing at least 40 kg• With a positive SARS-CoV-2 antigen or PCR test and within 10 days of symptom onset• High risk of disease progression
	
High risk is defined as patients who meet at least one of the following criteria:
 
• Are \geq 65 years old• A Body Mass Index (BMI)>25, or if age 12–17, BMI $\geq 85^{\text{th}}$ percentile• Pregnancy• Have chronic kidney disease• Have diabetes• Have immunosuppressive disease• Are currently receiving immunosuppressive treatment• Cardiovascular disease (including congenital heart disease) or hypertension• Chronic lung disease• sickle cell disease• neurodevelopmental disorders (e.g., cerebral palsy) or other conditions that confer medical complexity (e.g., genetic, or metabolic syndromes and severe congenital anomalies)• a medical-related technological dependence, for example, tracheostomy or gastrostomy)
	
The EUAs note that other medical conditions or factors (for example, race or ethnicity) may also place individual patients at high risk for progression and authorization of mAb treatment under the EUA is not limited to the medical conditions or factors listed above.

Exclusion Criteria	
These criteria are as per the FDA EUAs for COVID-19 mAbs as of April 2021.
 
• Are hospitalized for the treatment of COVID-19• Require oxygen therapy for the treatment of COVID-19• Require an increase in baseline oxygen flow rate due to COVID-19 in those on chronic oxygen therapy due to underlying non-COVID-19 related comorbidity• Have a known hypersensitivity to any antibody ingredient
Primary evaluation metric	Total hospital free days at 28 days

